8.5 Serological and ancillary testing

Blood samples (10 ml heparin plasma and 5.5 ml EDTA plasma) will be collected to detect the presence of antibodies (specific immune response) against SARS-CoV-2 antigenic proteins (e.g. Roche, Abbott). Specifically, all participants will be offered to receive the results for the following analytes in acknowledgment of their participation in the study: blood cell count, C-reactive protein, HbA1c, cholesterol, triglycerides, LDL cholesterol, HDL cholesterol, gamma-glutamyl-transferase, creatinine along with

formula-derived creatinine, vitamin D. Backup samples will be collected to determine ancillary parameters like inflammatory markers, and micronutrients and vitamins.

9. Observation Period

NIS schedule:

Start of the patient recruitment: February 1, 2021
End of the observation period: March 31, 2021
Final report: May 31, 2021

10. Data analysis and statistical methods

A database of the pseudonymized data and results will be generated. We hypothesize that each of the antigen tests has a sensitivity and specificity of 1.0 in relation to RT-PCR which will be considered as the reference test. A p value of less than 0.05 will be required to consider each of the two rapid tests equivalent to RT-PCR.

With the aid of *power calculations for chi-square tests* for two degrees of freedom, required type I error probability equal to 0.05, required (1-type II error probability) equal to 0.8 and required effect size equal to 0.1 (small effect size in the sense of (4)) we obtain a number of at least $N=964$ observations for consecutive testing of incoming patients in order to fulfill our requirements on significance and power to answer the first research question. Because of the expected number of around 10% positive out of 1000 cases, the assumption of a chi-square distribution is permissible.

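### Section 10: the 10% positivity argument does not support a chi-square test of sensitivity and specificity 1.0, and the association test it could support cannot show equivalence

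*Combined protocol and SAP*

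**What the plan says.** Section 10 (Data analysis and statistical methods) sets the hypothesis: "We hypothesize that each of the antigen tests has a sensitivity and specificity of 1.0 in relation to RT-PCR". RT-PCR is the reference. The decision rule follows: "A p value of less than 0.05 will be required to consider each of the two rapid tests equivalent to RT-PCR".

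The sample size for the first research question is a chi-square power calculation "for two degrees of freedom", with type I error 0.05, power 0.8 and effect size 0.1, giving at least 964 observations. The distributional assumption is defended in one sentence: "Because of the expected number of around 10% positive out of 1000 cases, the assumption of a chi-square distribution is permissible".

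The section then adds a second question, whether sensitivity differs between two indication groups, and extends enrolment to 2000 for it. No test is named for that comparison.

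Section 10 does not name the null hypothesis, the table, the chi-square statistic or the source of the two degrees of freedom. It gives no confidence interval, exact method or equivalence margin.

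**The concern.** A large-sample chi-square needs adequate expected counts in the cells of the table being tested, under the null being tested. The plan argues from the number of positives, which is one margin of the table. Sensitivity is decided by how many RT-PCR positives the antigen test misses, and specificity by how many RT-PCR negatives it flags. If the plan's hypothesis is true, both of those cells are empty.

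The sentence therefore has two possible readings. Either it defends a test of 1.0/1.0, which it cannot do, or it defends a test whose counts are sound but which does not measure what Section 10 sets out to establish. In the second case the p < 0.05 rule could label a poor antigen test equivalent to RT-PCR. Section 5 expects the results to influence current recommendations on antigen testing, so that label would matter.

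**Working it through.** **Inputs.** From Section 10: sensitivity = specificity = 1.0; alpha 0.05; power 0.8; effect size w = 0.1; 2 df; about 10% positive in 1000; 2000 participants in the extended study. Every sensitivity or specificity below 1.0 used here, and every group split, is an illustrative assumption.

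**1. The plan's own figure.** Find λ so that P(χ²(2 df, λ) > 5.991) = 0.80. This gives λ = 9.635, and N = λ/w² = 9.635/0.01 = 963.5, rounded up to 964. The stated number reproduces. With 1 df the answer would be 785 and with 3 df 1091, so two degrees of freedom were really used. A single 2×2 table has only one.

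**2. Expected cells under 1.0/1.0.** For N = 1000:

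- true positives: 1000 × 0.10 × 1.0 = 100
- false negatives: 1000 × 0.10 × (1 − 1.0) = 0
- false positives: 1000 × 0.90 × (1 − 1.0) = 0
- true negatives: 1000 × 0.90 × 1.0 = 900

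At N = 2000 the cells are 200, 0, 0 and 1800. The Pearson sum of (O − E)²/E has zero denominators in the two cells that matter. McNemar's statistic (b − c)²/(b + c) is 0/0. A single discordant result already contradicts the hypothesis, and no prevalence changes this.

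**3. Test of association in a 2×2 table.** With both margins at 10%, E = row × column/N gives 100 × 100/1000 = 10, then 90, 90 and 810. These counts are adequate. The question is another one, though. Perfect agreement gives χ² = 1000, that is w = 1.0 and not 0.1. Assume sensitivity 0.60 and specificity 0.99: the cells are TP 60, FN 40, FP 9, TN 891, with 69 antigen-positive and 931 antigen-negative. The smallest expected count is 100 × 69/1000 = 6.9, and

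χ² = 1000 × (60 × 891 − 40 × 9)² / (100 × 900 × 69 × 931) = 487.7, p ≈ 5e-108.

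With sensitivity 0.30 and specificity 0.98 (cells 30, 70, 18, 882), χ² = 154.4 and p ≈ 2e-35. Both would pass a p < 0.05 rule.

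**4. Three tests by positive/negative.** This table does have 2 df, with expected counts of 100 and 900 per test, again adequate. But the three results come from the same participant, so the rows are not independent. It also compares positivity rates only: a test with 40 misses and 40 false positives still shows 100 − 40 + 40 = 100 positives. Here p < 0.05 would indicate a difference, not equivalence.

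**5. Paired comparison with few discordances.** Four discordances in one direction give χ² = (4 − 0)²/4 = 4, p = 0.046; the exact p is 2 × 0.5⁴ = 0.125. Five give 0.025 against 2 × 0.5⁵ = 0.063. The call at 0.05 changes in both cases.

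**6. What intervals would show.** With no errors in n, the two-sided 95% Clopper-Pearson lower bound is 0.025^(1/n): 0.964 for 100/100 and 0.996 for 900/900; with the extended sample, 0.982 for 200/200 and 0.998 for 1800/1800. The Wilson bound for 100/100 is 100/(100 + 1.96²) = 0.963. The p of 5e-108 in step 3 conveys none of this.

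**7. Indication-group comparison, if Pearson were used.** Exact size at nominal 5%, enumerating two binomials with 200 positives in total:

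| Common sensitivity | 100/100 | 160/40 |
|---|---|---|
| 0.80 | 5.1% | 5.1% |
| 0.90 | 5.2% | 4.7% |
| 0.95 | 4.4% | 3.5% |
| 0.98 | 4.0% | 6.0% |
| 0.99 | 1.4% | 8.8% |

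At 0.99 the chance of no miss at all is 0.99²⁰⁰ = 13%. Section 10 expects the two groups to supply about 90% of positives; with 180 the pattern is the same (1.1% for 90/90 and 9.0% for 144/36 at 0.99). Fisher's test is not a free remedy: at 100/100 it lowers power from 85% to 77% for 0.99 against 0.90.

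**The case against.** The strongest reply is that Section 10 never makes 1.0/1.0 the null. Because p < 0.05 is to mean equivalence, perfect agreement reads as the hoped-for result, and the null may be no association. The expected counts are then sound, as step 3 shows, and two degrees of freedom could point to the table in step 4, where they are sound too. This stands. A reader might infer from the empty cells that p-values from the planned chi-square are unreliable throughout; the documents do not support that, because they do not say which test is meant.

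A reader might also infer that poor normal-approximation intervals are planned, or that the group comparison is compromised. The plan states no intervals and names no test for that comparison. At sensitivities of about 0.80 to 0.95, Pearson is adequate there. Nor does the approximation fail at every realistic specificity: 1782 negatives correctly classified of 1800 give a normal interval of 98.54-99.46% against an exact 98.42-99.41%.

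What the reply does not do is rescue the sentence. The readings with adequate counts are those in which the p-value does not address sensitivity or specificity.

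**Conclusion.** The point holds in a limited form. The 10% argument does not justify a chi-square test of sensitivity and specificity 1.0, because both error cells have expected count 0 under that hypothesis whatever the sample size. This follows from the plan's own figures. Read as a test of association, the chi-square is numerically valid but would certify as equivalent a test with an assumed sensitivity of 0.60. That result depends on the illustrative values, although the conclusion is not sensitive to them: 0.30 with 0.98 passes as well.

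The deeper gap is that the null, table and statistic are undefined and no minimum performance is stated, so no chi-square p-value here can show equivalence. The small-sample failure of McNemar matters only if discordances are few. For the indication-group comparison, marked distortion of Pearson's size appears only at sensitivities of about 0.99 or more.

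**What to change.** In Section 10:

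- Delete the sentence that defends the chi-square distribution.
- Base the first research question on the sensitivity and specificity of each antigen test against RT-PCR, each with a Clopper-Pearson or Wilson 95% confidence interval.
- Replace the p < 0.05 rule by a comparison of the lower confidence limits with minimum acceptable values that the sponsor states before the data are seen. Exact intervals alone, without such a value, would not settle equivalence.
- Where results from the same participant are compared, use exact McNemar.
- For the indication-group comparison, name the test. Pearson is adequate at sensitivities of about 0.80 to 0.95; specify an exact unconditional test such as Boschloo's for the case of very few misses. Fisher's test should not be mandated, given its loss of power.

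The cost is a few sentences and slightly wider intervals. No additional data collection is needed for the estimates. Once minimum values are chosen, the sponsor should check whether the expected 100 or 200 positives give enough precision, since 964 was not derived for that purpose.

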It is therefore hoped that rapid antigen tests can support diagnosis of COVID-19 in people who have the first symptoms. In the USA, some tests have received authorization for diagnostic testing in symptomatic individuals, within 5-7 days from the onset of symptoms (3).

5. Risks and benefits

Three nasopharyngeal swabs and one blood sample will be obtained from each of the participants. Antigen tests, RT-PCR and serological and ancillary laboratory tests are performed in this study.

Risks from nasopharyngeal swabs: The biggest risk is discomfort. Rarely - 1 in thousands — the person receiving the swab passes out from being super sensitive or gets a mild nosebleed.

Risks from blood draw: The risks of venipuncture include Minor bruising at the site where the blood is taken and hematoma (12 % approximately), with minor bruising being the most common reaction. Significant complications (defined as cellulitis, phlebitis, diaphoresis, hypotension, near syncope, syncope) are observed in approximately 3.5% of patients. The most frequent single significant complication is hypotension at a frequency occurred of approximately 2.6%. Syncope is seen in less than 1% of patients. Other serious local reactions such as cellulitis or phlebitis are very rare (Galena HJ, J. Fam. Pract. 1992 May;34(5):582-4). Blood sampling is therefore conducted in each of the study sites under the surveillance of a board licensed physician.

Benefits to public health: Point of care antigen testing is an integral component of the current national testing strategy serving for preventing of the spread of COVID 19
https://www.bundesgesundheitsministerium.de/fileadmin/Dateien/3_Downloads/C/Coronavirus/Nationale_Teststrategie_kurz_041220.pdf

There is, however, significant uncertainty as to the reliability of antigen testing in comparison to the gold standard of testing, rt-PCR. To the authors' knowledge a prospective, sufficiently sizeable and challengeable evaluation of antigen testing under

practice conditions has not been completed so far. The current study is intended to close this gap. Its results are urgently required and will have immediate impact on current recommendations for using antigen testing. In particular, it will demonstrate weaknesses and strengths of antigen testing and will allow to outweigh potential technical limitations of antigen testing compared to rt-PCR against the advantage of short-term availability of test results.

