We will also address the question whether different pre-test probabilities will affect the sensitivity of the antigen tests. We expect two major indication groups with different pre-test probabilities contributing approximately 90 percent of the rt-PCR positive samples: a) participants admitted for rt-PCR testing by a physician b) participants seeking for rt-PCR testing upon recommendation by health care authorities/contact persons. A total of approximately 200 rt-PCR samples will be required to detect a statistically significant difference between these two groups at a type 1 error of 0.05 and a statistical power of 0.80. To answer this second question, we will extend the study to 2000 participants.

11. Ethics

The study protocol will be submitted to the Ethics Committee the Medical Faculty Mannheim, University of Heidelberg and the study will not begin until written permission is obtained. The study will be conducted in accordance with German law, EU Clinical Trial regulations and the Declaration of Helsinki on the ethical principles of clinical research.

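### The second research question credits pre-test probability with any sensitivity difference between referral groups, without stratifying for case mix and without planning the predictive values that depend on it directly

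*Combined protocol and SAP*

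**What the plan says.** The second research question is in Section 10: "We will also address the question whether different pre-test probabilities will affect the sensitivity of the antigen tests". The plan makes it concrete through referral route: "We expect two major indication groups with different pre-test probabilities contributing approximately 90 percent of the rt-PCR positive samples". One group is sent by a physician; the other comes on the recommendation of health authorities or contact persons.

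The size for this question is given as "A total of approximately 200 rt-PCR samples will be required to detect a statistically significant difference between these two groups", with alpha set to 0.05 and power to 0.80. It is the stated reason for the larger enrolment: "we will extend the study to 2000 participants", against at least 964 for the first question.

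The only accuracy measures named are in the first hypothesis: "each of the antigen tests has a sensitivity and specificity of 1.0 in relation to RT-PCR". Predictive values appear nowhere in the supplied text. No stratification or adjustment of the group comparison is stated.

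Two other places bear on this. The background text before Section 2 says antigen tests miss more infections when there is less virus, and may be unreliable in asymptomatic people, in the first days of infection and beyond 5-7 days from symptom onset. Section 8.1 collects COVID-19 symptoms and their time of onset.

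**The concern.** Sensitivity conditions on a positive RT-PCR. If the positives in two groups are alike, the groups have the same sensitivity whether 5% or 20% of those tested are positive. What can move sensitivity between referral groups is the kind of positive each contains, and the protocol's background text names that mechanism. The groups are formed by referral, not by randomisation (only swab order is randomised), so their positives may well differ in viral load, symptom status and time since onset.

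As worded, a significant difference would be presented as an effect of pre-test probability. A null result could be taken to mean that pre-test probability is unimportant for antigen testing, although it says nothing about predictive values. Section 5 expects that the results "will have immediate impact on current recommendations for using antigen testing". Anyone acting on such recommendations in a given referral group needs the chance that a positive or negative result agrees with RT-PCR, and the plan does not commit to reporting it.

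**Working it through.** **1. The plan's own figures.**
- First question: chi-square power with 2 degrees of freedom, effect size w = 0.1, alpha 0.05, power 0.80. The required noncentrality is 9.635, and 9.635 / 0.1² = 963.5, rounded up to 964. This reproduces the stated number.
- Second question: about 200 cannot be derived from the stated inputs, because no effect size is given. With 1 degree of freedom and an assumed w = 0.2, 7.849 / 0.2² = 196.2, rounded up to 197, which is close. Reading the 200 as RT-PCR positives fits the expected positivity ("Because of the expected number of around 10% positive out of 1000 cases"): 10% × 2000 = 200. The point made here does not depend on this figure.

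**2. Can case mix alone give a significant difference at the planned size?** All of these inputs are assumptions.
- Sensitivity is 0.90 at high and 0.40 at low viral load, the same in both groups.
- Of the positives, 80% in one group and 40% in the other have high load.
- Crude sensitivity, first group: 0.80 × 0.90 + 0.20 × 0.40 = 0.80.
- Crude sensitivity, second group: 0.40 × 0.90 + 0.60 × 0.40 = 0.60.
- Positives in the two groups: 90% × 200 = 180, so 90 each if split equally.
- Power of a two-sided 5% comparison of 0.80 with 0.60 at 90 per group: about 0.84.
- With a milder imbalance, 80% against 60% high load, crude sensitivity is 0.80 against 0.70 and power about 0.34.

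Group positivity enters none of these sensitivities.

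**3. What pre-test probability does change.** With sensitivity Se, specificity Sp and group positivity p:

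PPV = Se·p / [Se·p + (1 − Sp)(1 − p)]

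NPV = Sp(1 − p) / [Sp(1 − p) + (1 − Se)p]

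Assume Se = 0.80 and Sp = 0.99 in both groups:

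| p | PPV | NPV |
|---|---|---|
| 5% | 0.0400 / (0.0400 + 0.0095) = 80.8% | 98.9% |
| 8% | 0.0640 / (0.0640 + 0.0092) = 87.4% | 98.3% |
| 10% | 0.0800 / (0.0800 + 0.0090) = 89.9% | 97.8% |
| 12% | 0.0960 / (0.0960 + 0.0088) = 91.6% | 97.3% |
| 20% | 0.1600 / (0.1600 + 0.0080) = 95.2% | 95.2% |

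Sensitivity is 80% in every row. The PPV gap is about 4 points for 8% against 12%, and about 14 points for 5% against 20%. Over Se 0.60-0.95 and Sp 0.97-0.995, PPV runs from 0.51 to 0.91 at 5% positivity and from 0.83 to 0.98 at 20%.

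**4. Precision of a group PPV.** With 90 RT-PCR positives among 900 participants in a group (10% positivity), the same Se and Sp give 90 × 0.80 = 72 true positives and 810 × 0.01 ≈ 8 false positives. For 72/80 = 90%, the exact 95% interval is about 81% to 96%.

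**The case against.** The strongest reply is that Section 10 already defines a sound comparison. It sets the sensitivity of each test in one referral group against the other, and the phrase about pre-test probability merely describes those groups. Sensitivity is a stated measure, and whether it varies with the kind of patient is a proper spectrum question. This stands. A reader might infer that the second question estimates the wrong quantity and that the extension to 2000 is therefore wasted. The documents do not support that: the comparison remains valid once its label is changed.

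Second, no passage says how a difference or a null result will be interpreted, and the background text shows that the authors know the spectrum mechanism. This also stands in part. Misattribution is likely from the wording, but not certain.

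Third, a reader might go further and say that any difference must be case mix. That is too absolute. If infection is the target and RT-PCR is imperfect, apparent sensitivity does move with prevalence. Assume antigen Se 0.80 and Sp 0.99, RT-PCR sensitivity 0.98, and independent errors given infection status. From 5% to 20% prevalence, apparent sensitivity goes from 0.785 to 0.797 if RT-PCR specificity is 0.999, and from 0.672 to 0.769 if it is 0.99. Section 10 takes RT-PCR as the reference, so the statement made here is conditional on that.

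Fourth, PPV and NPV can be had from the same 2×2 tables, since enrolment is consecutive and every participant has all three tests. True; no information is lost. But only pre-specification ensures that they are reported.

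**Conclusion.** The point holds as one of wording, analysis and reporting. The second question attributes to pre-test probability a difference that, with RT-PCR as the reference, pre-test probability does not by itself produce. The comparison is unstratified although the relevant covariates are collected, and the measures that depend directly on pre-test probability are not planned. It should be corrected, but it does not invalidate the study.

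Its size is uncertain. The documents give about 10% positivity overall and nothing by group, so the 14-point PPV gap should not be read as expected: it rests on an assumed fourfold difference in positivity, and a contrast of 8% against 12% gives about 4 points. The case-mix example shows that a spurious attribution could reach significance at the planned size, not that it will. Sensitivity, specificity, viral-load mix and the equal split of positives are all assumptions.

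**What to change.** In Section 10:

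1. Reword the second question as: *whether the sensitivity of each antigen test differs between the two indication groups*. Attribute nothing to pre-test probability, and nothing to case mix either, since that would replace one untested cause with another.
2. Report the group comparison crude, and also stratified or adjusted by symptom status, with an asymptomatic category, and by days since onset among symptomatic participants. Onset time alone is not enough, because asymptomatic participants have none. Both variables are collected under Section 8.1. The documents do not say that viral load is recorded, so some case-mix difference may remain after adjustment.
3. Report PPV and NPV against RT-PCR for each test with exact 95% confidence intervals, overall and by indication group, beside that group's RT-PCR positivity.

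The cost is a change of wording, a stratified analysis and one further table, all from planned data, with no added patients or measurements. The downside is wide intervals within strata and for group PPV (roughly 81% to 96% in the example above), so these results should be presented as estimates and not as tests.

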11.1 Patient information and Informed Consent

The objective, nature and extent of the document must be explained in writing to every patient before he or she is included in the study (Appendix 1). The patient must not be included unless he or she has given written consent (Appendix 2). Patients will have the right to refuse to participate or to withdraw from the study for any reason and at any stage without affecting the quality or accessibility of their health care.

